9.5 Engineer's visits

Engineers will conduct a screening visit for potential trial participants in order to assess the suitability of their home for the installation of a water softener. A standard checklist will be prepared for this purpose. Any households which are not able to have a unit installed (for whatever reason) will not be enrolled into the study. The pre-recruitment visit will also assess the likely salt requirements of the family, and test water hardness.

If randomised to Arm A, an installation visit will take place as soon as possible following randomisation to treatment (ideally within 10 working days).

For the active treatment group parents will be sent information about how to bypass the unit and asked to do this immediately they return home after their child's 12-week assessment visit. Units will subsequently be removed by the water engineer as soon as possible (ideally within 5 working days) to ensure that the units cannot be turned on again during the final 4-week non-intervention period. If the family chooses to purchase a unit at a reduced price (£446.50) a unit will be reinstalled after they have completed the final 4-week non-intervention period of the study. Families in the active treatment group will send samples of water for hardness testing on a weekly basis throughout the 12 week period when the unit is installed. Those allocated to delayed treatment will receive an active unit at 12 weeks. This will then be removed after week 16 unless the family decides to purchase the unit. Families in the delayed treatment group will send samples of water for hardness testing on a weekly basis from weeks 13 to 16 inclusive.

10. STATISTICS

10.1 Statistical design

Analyses have been planned in order to place emphasis on objective outcomes that are less likely to be influenced by the potential bias inherent in a single-blind study. Nevertheless, a variety of additional tools are to be used that reflect more closely the disease process throughout the study period. Some of these are relatively objective indicators of disease activity (such as nocturnal movement and treatment application), whilst others reflect subjective concepts (such as self-reported symptoms in the POEM), in order to capture the many health-related dimensions affected by eczema.

The planned analyses should answer the following questions:

- 1. Does exposure to softened water for 12 weeks improve the symptoms and severity of eczema, compared to standard care?
- 2. Does softened water improve quality of life for patients and their carers?
- 3. Are water softeners a cost-effective treatment for children with atopic eczema?

In addition, tertiary analyses will explore the following parameters:

4. How quickly the benefits of softened water become evident.

5. How quickly the benefits of softened water are lost once treatment is stopped.

The main intention-to-treat analysis will be conducted at 12 weeks. An additional per protocol analysis will also be conducted for the primary outcome in order to test the proof of concept.

A sub-group analysis will also be conducted based on the presence or absence of mutations on the gene filaggrin (*see* section 12). Mutations on the filaggrin gene have been associated with dry skin and may therefore be a useful predictor of treatment response.

10.2 Sample Size estimate

Sample size estimates are based on other published data relating to the use of SASSAD in patients recruited in secondary care¹⁵, ⁵. Based on a minimum clinically relevant difference of 20% in the change in SASSAD score between the 2 groups, and assuming a mean baseline SASSAD score of 20 with a standard deviation in change scores of 10 ¹⁵, a sample size of 310 children will provide 90% power, assuming a significance level of 5% and attrition rate of 15% (see planned interventions section). Sample size estimates based on the results of the pilot study, support this sample size estimate.

10.3 Primary analyses

♦ Change in disease severity (SASSAD) at 12 weeks compared to baseline, will be assessed using Student's t-test. An adjusted analysis will also be conducted including the stratification variables of eczema severity, age and recruiting centre.

In order to aid the clinical interpretation of these data, the number needed to treat (NNT) assuming a range of improvements in SASSAD scores will also be presented ($\geq 20\%$, $\geq 50\%$ and $\geq 75\%$ improvement).

10.4 Secondary analyses

- ♦ The proportion of time spent moving during the night will be compared using Student's t-test.
- ♦ The proportion of participants reporting either good or excellent improvement in disease severity on the global assessment scale will be analysed using a chi-squared analysis.
- ♦ A Student's t-test will be used to assess the difference in the number of grams of topical treatment applied.
- ♦ POEM scores will be compared at 12 weeks using Student's t-test.
- A Student's t-test will be used to assess differences in the number of Totally Controlled Weeks and Well Controlled Weeks throughout the study period.

- ♦ Mean scores on the Dermatitis Family Impact Scale and Quality of Life scores will be compared using a Student's t-test.
- ♦ Predictors of response model. Factors to be included in the model will be prespecified prior to analysis, but will include baseline eczema severity, previous treatment history, water hardness at baseline, prior belief relating to the benefits of softened water, demographic variables and filaggrin status (*see* Section 12).

10.5 Tertiary analyses

- ♦ Changes in SASSAD at 4 weeks will be assessed using Student's t-test.
- ♦ For the within group analyses, mean change in disease severity (SASSAD) at week 4 (relative to baseline) compared to mean change in disease severity at week 16 (relative to week 12) will be analysed using a paired samples t-test. These analyses will be used to explore speed of onset and possible carry-over effects.

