6.3 Further exploratory analyses

In addition to the main outcomes listed above, further exploratory analyses are planned as follows

• Difference in mean change in disease severity (SASSAD) at 4 weeks compared to

baseline. This outcome is included in order to capture speed of onset of benefit.

- Further within person analyses will be conducted comparing outcomes collected during the final 4-week period (12 to 16 weeks), with those collected during the initial 4 weeks of the study (0 to 4 weeks). Data collected for the active treatment group will provide an indication of the likely carry-over effect of this intervention, which will be useful in planning the design of future trials in this area. Data collected for the delayed treatment group will inform the analysis regarding speed of onset of improvement.
- Predictors of response model including baseline factors such as filaggrin status (see later section), baseline eczema severity, water hardness, swimming activity and time away from the home).

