7.1 Inclusion criteria

- Children aged 6 months to 16 years at baseline, with eczema as defined by the UK refinement of the Hanifin and Rajka diagnostic criteria ¹⁴.
- Eczema present at time of assessment (minimum SASSAD score of 10).
- Baseline water hardness of >200 mg/L of calcium carbonate.
- Home suitable for the installation of a water softening device (as assessed by water engineer)

Only one child will be enrolled per family. The choice as to which child becomes involved will be made by the parents and children involved, taking into account the inclusion criteria above.

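### Protocol 10.5's paired t-test of the week 0–4 against the week 12–16 SASSAD change cannot separate kept from lost benefit; the SAP omits it without withdrawing it and has no SASSAD estimate of carry-over

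*Combined protocol and SAP*

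**What the plan says.** Protocol section 3 sets two exploratory questions for the last four weeks: how fast benefit appears in the delayed group (B), and how fast it goes in the active group (A) once the unit is removed. Protocol 6.3 compares weeks 12–16 with weeks 0–4 within person and says: "Data collected for the active treatment group will provide an indication of the likely carry-over effect of this intervention".

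Protocol 10.5 gives two analyses. The first is a comparison at week 4: "Changes in SASSAD at 4 weeks will be assessed using Student's t-test". The second is within group. The week-4 change from baseline is set against the later change: "mean change in disease severity at week 16 (relative to week 12) will be analysed using a paired samples t-test". Its purpose follows: "These analyses will be used to explore speed of onset and possible carry-over effects".

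SAP 10.3 differs. For onset it lists the week-4 SASSAD t-test, a one-sample t-test on weeks 12–16 in the delayed group, and plots of daily bother scores. For carry-over it lists only a graph of daily bother scores in the immediate group. The paired test does not appear. SAP 3.3 makes the tertiary analyses conditional on a beneficial effect being found; Protocol 10.5 has no such condition.

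**The concern.** A paired t-test of two changes asks whether they are equal. The carry-over question in Group A is whether the week 12–16 change is near zero (benefit kept) or positive (benefit lost). The onset question in Group B is whether the week 12–16 change is negative. Neither is a statement about equality with the week 0–4 change.

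A second difficulty concerns the reference period. Entry requires a minimum score: "Eczema present at time of assessment (minimum SASSAD score of 10". Baseline scores are therefore selected upwards and may fall by week 4 without any treatment, while week-12 scores are not selected. Such a fall enters the week 0–4 change only, or mostly. It can make the two periods differ when softening does nothing, and it can offset a real onset in Group B.

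The protocol wants these results for planning later trials. A p-value from this test could be reported as evidence about carry-over when it carries none.

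**Working it through.** **Inputs from the documents.** Protocol 10.2 gives the effect, "minimum clinically relevant difference of 20% in the change in SASSAD score between the 2 groups", and the scale, "assuming a mean baseline SASSAD score of 20 with a standard deviation in change scores of 10". The effect is 0.20 × 20 = 4 points. Significance is 5%, taken as two-sided; attrition is 15%; allocation is 1:1.

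**The plan's own figure.** n per arm = 2 × (1.960 + 1.282)² × 10² / 4² = 131.3, so 132. Both arms: 264. Allowing for attrition: 264 / 0.85 = 310.6, so 311. The plan says "a sample size of 310 children will provide 90% power", which is reproduced to within one child. Evaluable per arm: 155 × 0.85 = 131.75, about 132.

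**Assumptions not in the documents.** The full 4-point effect is reached within four weeks, and loss, if it occurs, is complete within four weeks. SD 10 applies to each 4-week change. The two changes have correlation ρ, taken as 0 and varied from −0.3 to 0.3. The entry fall is r, taken as 0 to 3 points.

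**The test.** D = (week 4 − week 0) − (week 16 − week 12). SD of D = 10 × √(2(1 − ρ)) = 14.14 at ρ = 0. SE = 14.14 / √132 = 1.231. The critical t value is 1.978. Negative changes are improvements.

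**Group A, no entry fall.**
- Benefit kept: changes −4 and 0, so D = −4. 4 / 1.231 = 3.25; rejection Φ(3.25 − 1.98) = 90%.
- Benefit lost: changes −4 and +4, so D = −8. 8 / 1.231 = 6.50; rejection about 100%.

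Both reject in the same direction. Over ρ = −0.3 to 0.3 the kept figure runs from 81% to 97%; the lost figure stays at about 100%.

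**With an entry fall (ρ = 0).** With no softener effect D = −r in either group. With a 4-point onset in Group B, D = 4 − r.

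| Entry fall r | Rejection, no effect | Group B power, 4-point onset | Group A, kept |
|---|---|---|---|
| 0 | 5% | 90% | 90% |
| 1 | 12% | 68% | 98% |
| 2 | 36% | 36% | 99.8% |
| 3 | 68% | 12% | about 100% |

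(A simulation gave 13% for the last Group B figure.) At r = 2, varying ρ from −0.3 to 0.3 moves both the no-effect rejection and the Group B power between 29% and 49%.

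**How large might r be?** A floor of 10 and a mean of 20 do not fix it; between-child and within-child spread are also needed. Illustrative models with an unselected SD of 8 to 10 and a correlation between visits of 0.3 to 0.7 give about 0.7 to 3.6 points. Serial correlation softens the result. With total SD 10, between-child SD 5 and a 4-week noise correlation of 0.6, the 12-week change still has SD 10.0, but the fall is 1.6 points, no-effect rejection about 25% and Group B power about 80%.

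**A simpler quantity.** The week 12–16 SASSAD change tested against zero has SE 10 / √132 = 0.870 and 95% CI half-width 1.978 × 0.870 = 1.7 points. Its power for a 4-point change is 99.6%. In a simulation with r = 2.6, this test in Group A rejected about 4% of the time with benefit kept and 99.8% with benefit lost, so it separates the two cases.

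**The case against.** The strongest reply is that the SAP is the operative plan. Protocol 8.3 has the results analysed under a plan finalised before the coded allocation is revealed, and SAP 10.3 has no paired test. Onset does not depend on the paired test in either document, because the randomised week-4 comparison is already planned in both. Under SAP 3.3 tertiary analyses follow only a beneficial result, so the no-effect rejection rates mostly describe analyses that would not be run. All of this stands, and it limits the point to a reconciliation and a small addition.

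It is also fair that reporting both mean changes beside the p-value would show −4 and 0 as different from −4 and +4. But that information comes from the week 12–16 change on its own, not from the planned test.

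Three stronger readings are tempting, and the documents do not support them:
- A reader might infer that the test will hide a real onset in Group B. That depends on an entry fall of unstated size; power is 90% with no fall and about 80% in the serially correlated setting.
- A reader might infer that Group A rejects whatever the truth. With no effect and no fall, rejection is 5%.
- A reader might infer that the trial will report this test. The SAP gives no sign of that.

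**Conclusion.** The point holds for the protocol text and for the gap left in the SAP. On the plan's own effect, SD and sample size, and without assuming any entry fall, the paired test in Group A rejects about 90% of the time if benefit is kept and about 100% if it is lost. Its p-value therefore cannot answer the carry-over question. This assumes the effect is complete within four weeks and the two changes are uncorrelated; other correlations leave the conclusion unchanged.

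The effect of entry selection is conditional. For an assumed fall of 0 to 3 points and uncorrelated changes, no-effect rejection runs from 5% to about 68% and Group B power from about 90% to about 12%, with milder results under serial correlation.

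Two defects remain. Neither document says that SAP 10.3 replaces the protocol's test. And the SAP examines carry-over only on bother scores that SAP 8.3 says the parent records, in families who know their allocation, although Protocol 10.1 puts the emphasis on objective outcomes and blinded nurses already score SASSAD at weeks 12 and 16. The matter is tertiary and exploratory.

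**What to change.** 1. Delete the paired test from Protocol 10.5 and the matching comparison in 6.3, and state that SAP 10.3 replaces them.
2. Keep the planned randomised week-4 SASSAD comparison as the onset analysis.
3. Add to SAP 10.3 the mean week 12–16 SASSAD change in each group with a 95% CI. Loss of benefit in Group A is then estimated on the blinded outcome.
4. Optionally add an exploratory sensitivity estimate of residual benefit in Group A: (A minus B at week 16) + (A minus B at week 4), each adjusted for baseline SASSAD. It is near zero if benefit is lost and near the full effect if it is kept, and entry regression cancels between randomised groups. State its assumption that four weeks of softening works equally in both groups; the installation and visit windows in Protocol Table 1 may strain this. State its precision too. With a visit SD of 10 and test–retest correlation 0.5 (both assumed), residual variance is 75 and residual correlation 1/3, so SE = √(2 × 75/132 × (2 + 2/3)) = 1.74 points and the 95% CI is about ±3.4. Power for a fully kept 4-point benefit is only about 63%.

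The cost is a wording change and a few lines of code on data already collected. The downside is a little more exploratory output, and the within-group changes in item 3 have no concurrent control, so calendar or seasonal drift cannot be excluded.

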11. COST-EFFECTIVENESS ANALYSIS

11.1 Objective:

• To assess the cost-effectiveness of installing a water softening unit in the homes of families who have a child with eczema, when compared with usual care.

The cost analysis will compare the overall costs for the intervention to usual care, measuring resource use such as primary care contacts, medication prescribed, secondary care contacts and patient costs. Health and family resource use data will be measured using participant diaries. Resource use will be valued using published unit costs (e.g. Curtis and Netten ¹⁶, BNF 2005, and NHS reference costs (http://www.dh.gov.uk/PolicyAndGuidance/OrganisationPolicy/FinanceAndPlanning/NHSReferenceCosts/fs/en)), and patient reported estimates. The costs to the NHS and patient will be reported separately as well as in combination.

The primary measures of effectiveness for cost analyses purposes will be the number of participants who show a \geq 50% improvement in SASSAD at 12 weeks compared to baseline. Secondary analyses will be conducted using continuous data from the SASSAD scale; the Dermatitis Family Impact Scale; and the generic measure of health utility as measured on the child version of the EQ-5D (for children aged 3–6 years, the proxy version will be used).

If non-dominance occurs an incremental cost-effectiveness ratio will be produced. Sensitivity analysis will be undertaken to test the robustness of results in the face of any uncertainties or assumptions made in the analysis. In particular, assumptions about the time period over which the difference in costs and difference in benefits are likely to be sustained. Where appropriate the change in health-related quality of life measured on the

EQ-5D will be multiplied by the expected duration of benefits from water softening in order to calculate the Quality Adjusted Life Years (QALYs) of the intervention group compared to the usual care group.

In addition to the cost effectiveness analysis, contingent valuation (CV) methodology will be employed to measure parental willingness to pay for the water softener device as a measure of benefit. CV methodology is now more widely used as a measure of benefit in the health care field ¹⁷. It is an important issue in the context of this study, since it is not clear at this stage who will, or should, pay for the device: the parent or the NHS. Willingness to pay will be asked pre-intervention at the recruitment visit to get an ex-ante hypothetical willingness to pay and again at week 12. At the end of the study, all participants will get the opportunity to purchase the device that they used in the study, thus giving us a measure of parental actual willingness to pay. This will enable us to test whether a hypothetical bias exists in health CV studies in this context.

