3. STUDY DESIGN

This is a single-blind, parallel group randomised controlled trial of 12-week duration, followed by a 4-week cross-over period (Figure 1). The study will be analysed as a parallel group study, but the final 4 week period will include exploratory analyses to explore within person effects. Specifically, these exploratory analyses will provide further information on (i) the speed of onset of benefit for the delayed treatment group, and (ii) on how quickly benefits are lost once treatment is removed in the active treatment group. Three hundred and ten children with moderate to severe eczema will each be enrolled into the study for a period of 16 weeks. Participants will be enrolled over a period of 18-20 months, starting in Spring 2007. The end of study is defined as being the final assessment visit of the last participant into the trial.

Figure 1: Study design

| | STUDY PERIOD = 16 weeks | | |
|---------|--|----------------|-------------------------|
| | 0 to 12 weeks | 12 to 16 weeks | |
| Group A | Usual eczema care + water softener installed (n = 155) | Unit removed | Option to purchase unit |
| Group B | Usual eczema care + delayed installation (n = 155) | Unit installed | at reduced cost |

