 - The intervention involves the entire household, so a quality of life scale appropriate to the family unit seems most appropriate.
 - It avoids the need to use two different age-specific dermatology quality of life scales (the Children's Dermatology Life Quality Index¹¹ and the Infants version of the same scale¹²).
- 7. Mean change in health related Quality of Life at 12 weeks. This will be captured using a generic measure of health utility (the children's version of the EQ-5D for children aged 7 years and over, or the proxy version of the EQ-5D for children aged 3 to 6 years ¹³).

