9. DATA COLLECTION

9.1 Data Collection Methods (summarised in Table 1)

9.1.1. Face-face interviews with the research nurse

These interviews will take place at baseline (recruitment visit), 4 weeks, 12 weeks and 16 weeks.

The visits will include the following:

- i. check of eligibility criteria (recruitment visit only)
- ii. baseline characteristics / demographics (recruitment visit only)
- iii. examining the child for disease severity (using the Six Area, Six Sign Atopic Dermatitis score)
- iv. eczema symptoms (POEM)
- v. interviewing the family for quality of life dermatitis family impact questionnaire and EQ-5D $\,$
- vi. willingness to pay for an ion-exchange water softener (recruitment and by letter sent at 10 -12 weeks)
- vii. digital image of nominated target lesion³
- viii.weighing medications.

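### The QALY rule (12-week EQ-5D change times duration of benefit) fixes no start point and ignores build-up before week 12, so it can overstate the QALY gain

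*Combined protocol and SAP*

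**What the plan says.** Protocol section 11.1 has the only QALY rule in either document. The sentence opens "Where appropriate the change in health-related quality of life measured on the" and continues "EQ-5D will be multiplied by the expected duration of benefits from water softening in order to calculate the Quality Adjusted Life Years", for the intervention group relative to usual care. It does not repeat a time point. Section 6.2, item 7, supplies one: "Mean change in health related Quality of Life at 12 weeks".

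Section 11.1 also plans sensitivity analyses for uncertainties and assumptions in general. The one it singles out is how long the differences in costs and benefits will last.

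The design in section 3 is a "single-blind, parallel group randomised controlled trial of 12-week duration, followed by a 4-week cross-over period". Table 1 allows up to 10 working days from day zero for the Group A unit to be installed. Section 10.1 lists "How quickly the benefits of softened water become evident" among the questions to be explored.

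On when EQ-5D is measured, section 9.1.1 says "These interviews will take place at baseline (recruitment visit), 4 weeks, 12 weeks and 16 weeks" and includes in the visit content "interviewing the family for quality of life dermatitis family impact questionnaire and EQ-5D", with no restriction by visit. Table 1 shows utility measures at baseline, 12 weeks and 16 weeks, and none at week 4.

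The SAP lists no EQ-5D endpoint and gives no QALY method.

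**The concern.** A change multiplied by a duration is a rectangle: the whole gain is credited for every week counted. A QALY gain is the area between the two arms' utility curves over time. The two agree only if the full gain is present throughout the weeks counted.

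Section 11.1 does not say whether the weeks run from day zero, from installation or from the point of full benefit. If they run from day zero, the rule credits a gain that cannot yet exist in full: randomised arms are expected to be equal at baseline, and a Group A home may have no unit for about two weeks. The plan itself treats the speed of onset as unknown. For a gain that rises to its week-12 level without overshooting it, the error during build-up can only favour the softener. It raises the QALY gain and, where the softener costs more, lowers the cost per QALY. Cost-effectiveness is objective ii in section 4 and question 3 in section 10.1.

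**Working it through.** The documents state no QALY figure, duration or horizon, so there is no figure of the plan's own to reproduce. The check compares the rule with the area under the curve.

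**Inputs from the documents.** EQ-5D change at 12 weeks (section 6.2); parallel comparison of 12 weeks (section 3); installation up to 10 working days, about 2 weeks, after day zero (Table 1).

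**Assumptions made here.** The duration is counted from day zero; the path of the gain between weeks 0 and 12 is varied; the gain is held at its week-12 level afterwards; horizons of 16 weeks, one year and two years are used for illustration.

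**Formulas.** Let d be the between-arm EQ-5D gain at week 12, H the horizon in weeks, and A the area over weeks 0 to 12 in units of d-weeks.

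- Rule: d × H / 52
- Area under the curve: d × (A + H − 12) / 52
- Ratio of rule to area: H / (A + H − 12), which does not depend on d

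**Straight-line rise over weeks 0 to 12.** A = ½ × 12 = 6.

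- 12 weeks: 12 / 6 = 2.00
- 16 weeks, gain held: 16 / 10 = 1.60
- One year: 52 / 46 = 1.13
- Two years: 104 / 98 = 1.06

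With an illustrative d of 0.10, the 12-week rule gives 0.10 × 12/52 = 0.0231 QALY, against 0.0115 by area. At one year it gives 0.100 against 0.0885. For a fixed positive cost difference, the cost per QALY would be halved at 12 weeks and 1 − 46/52 = 11.5% too low at one year.

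**Other onset paths.**

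| Path of the gain | A | Ratio at 12 weeks | Ratio at one year |
|---|---|---|---|
| Full gain from day zero | 12 | 1.00 | 1.00 |
| Linear to full gain by week 4 | 10 | 1.20 | 1.04 |
| Unit in at week 2, immediate effect | 10 | 1.20 | 1.04 |
| 75% of gain at week 4, rest by week 12 | 8.5 | 1.41 | 1.07 |
| Linear over weeks 2 to 6 | 8 | 1.50 | 1.08 |
| 50% of gain at week 4, rest by week 12 | 7 | 1.71 | 1.11 |
| Linear over weeks 0 to 12 | 6 | 2.00 | 1.13 |
| Linear over weeks 2 to 12 | 5 | 2.40 | 1.16 |

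The last row is the slowest onset taken as plausible, not a mathematical limit. A gain that appeared only at week 12 would leave the 12-week ratio undefined and give 52 / 40 = 1.30 at one year.

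**Duration counted from full benefit instead.** With the straight-line rise, full benefit arrives at week 12. To one year the rule then credits 52 − 12 = 40 weeks against a true 46, so it understates (40 / 46 = 0.87).

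**The case against.** The strongest reply is that the documents never say the gain is credited from day zero. The text speaks of the duration of benefits, which in ordinary use runs while benefit exists. It follows directly on the remark about how long benefits last, so it reads as an extrapolation rule for a household device rather than a within-trial calculation. It is also qualified as applying only where suitable. A reader might infer that the plan overstates QALYs two-fold as a matter of fact. The documents do not support that: the start point, the horizon and the straight-line path all have to be supplied from outside.

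Three further points carry weight. The general wording on sensitivity analysis does not exclude onset, so it would be wrong to say that the plan rules out testing it; onset is simply not named. If the benefit fades only gradually after the unit is taken out at week 12, the fading tail offsets part of the excess: with a straight-line rise, the 12-week rectangle over the full area is 12 / 8 = 1.5 for a 4-week fade and 12 / 12 = 1.0 for a 12-week fade. And at long horizons the discrepancy becomes small.

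This reply removes the unconditional figures but not the gap. On either reading of the start point, the rule matches the area under the curve only if onset is immediate. Under a straight-line rise to one year, two analysts following the same sentence could credit 52 weeks or 40, where the area is 46.

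**Conclusion.** The point holds in conditional form. The QALY rule is a rectangle with an undefined start and no provision for build-up, and the SAP does not fill the gap. If the duration is counted from day zero and the gain rises linearly to week 12, QALYs are overstated two-fold over the 12-week comparison and by about 13% at one year. Across plausible onset paths, still counting from day zero, the overstatement is 0 to 140% at 12 weeks and 0 to about 16% at one year. It is nil if benefit is immediate. Counting from full benefit gives no overstatement, but leaves out the build-up.

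The two-fold figure belongs to the 12-week comparison, not to the 16-week study period, where the same assumptions give 1.60. The one-year horizon is an assumption made here.

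A reader might also infer that the whole economic evaluation is compromised. It is not: the primary effectiveness measure in section 11.1 is the number of children with at least 50% improvement in SASSAD, and EQ-5D enters only in secondary analyses. The matter is worth correcting before analysis, but its reach is limited to the QALY result.

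**What to change.** Replace the rule in section 11.1 with the following.

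1. Compute within-trial QALYs for each child with EQ-5D data as the area under the utility curve over weeks 0 to 12 by the trapezium rule, using every EQ-5D visit in that period. With utilities u at weeks 0 and 12 only, this is ½ × 12 × (u0 + u12) / 52. With week 4 as well, it is [½ × 4 × (u0 + u4) + ½ × 8 × (u4 + u12)] / 52.
2. Compare arms with adjustment for baseline utility.
3. Report any extrapolation beyond week 12 as a separate, labelled term: the week-12 between-arm difference times the assumed further duration.
4. Name speed of onset among the sensitivity analyses. A two-point trapezium itself assumes a straight line, so this is needed even after the change.
5. Reconcile section 9.1.1, which implies EQ-5D at week 4, with Table 1, which shows none. If a week-4 value exists, it replaces much of the onset assumption with data.

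The change takes a few sentences and needs no data beyond the EQ-5D visits already planned. Its downside is that the stated QALY gain may become less favourable to the softener.
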